## 2.5 Study Design

This is an open-label, randomized, three-arm, directly observed therapy, pharmacokinetic study of TAF-FTC PrEP among low-risk HIV-uninfected non-pregnant cisgender women. HIV-uninfected non-pregnant cisgender women at low risk for HIV will be randomly assigned to 1 of 3 dosing frequencies of DOT TAF-FTC PrEP (**Figure 3**): 2, 4, or 7 doses per week to help differentiate poor and modest from perfect adherence (**Figure 3**).

Enrollment will continue until 54 non-pregnant evaluable participants (i.e., participant with completed data on dosing and PK samples) are enrolled.

- **Group #1: "7 doses per week or Perfect Adherence arm"** — cisgender women will receive a single tablet of co-formulated 25 mg TAF/ 200mg FTC once daily (7 doses per week).
- **Group #2: "4 doses per week or Moderate Adherence arm"** — cisgender women will receive a single tablet of co-formulated 25 mg TAF/ 200mg FTC tablet on Monday, Tuesday, Thursday, Friday.
- **Group #3: "2 doses per week or Poor Adherence arm"** — cisgender women will receive a single tablet of co-formulated 25 mg TAF/ 200mg FTC tablet on Monday and Tuesday

### Justification for non-daily dosing of PrEP groups:

In this study we propose to randomize cisgender women to non-daily dosing of PrEP (2, or 4 doses per week). The non-daily dosing is needed to investigate and demonstrate dose proportionality of TFV and TFV-DP concentrations. The adherence-concentration thresholds derived from this dosing frequency will help guide appropriate interpretation of adherence to TAF-based PrEP in clinical studies and implementation programs of PrEP. To minimize the risk of HIV infection in the non-daily dosing groups, as detailed in the eligibility section, only non-pregnant cisgender women at low HIV risk based on Kenya

guidelines will be enrolled and participants will receive a full package of HIV prevention, including risk reduction counseling, condoms and STI treatment at each visit. We will also perform monthly HIV testing. We will closely monitor the frequency of adverse events, including emergent HIV seroconversion (expected to be very rare) between groups.

## 2.6 Enrollment Targets

A cohort of up to 54 cisgender women who meet the inclusion and exclusion criteria described in Section 3 below will be enrolled at the KEMRI Thika Research Site, in Thika, Kenya. Enrollment will continue until 54 evaluable cisgender women are enrolled who agree to use PrEP at the Enrollment visit. Cisgender women who accept PrEP will be randomized 1:1:1: **2, 4, or 7** DOT doses per week to help differentiate poor and modest from perfect adherence.

## 3 STUDY POPULATION

We will enroll a novel cohort of up to 54 healthy, HIV-uninfected non-pregnant Kenyan cisgender women volunteers 18-30 years to establish benchmark adherence-concentration thresholds for TAF-based PrEP. Participants will be selected for the study according to the criteria in Sections 3.1 and 3.2. They will be recruited, screened, and enrolled as described in Section 3.4.

### 3.1 Inclusion Criteria

This study will enroll young Kenyan cisgender women (aged 18-30 years old). Cisgender women bear the greatest burden for HIV infection; thus, the study will focus solely on cisgender women. HIV incidence is greatest in younger cisgender women ages 15-24, as is interest in accumulating PrEP data from Kenya. The age limitation on enrollees into the study reflects that clinical and epidemiologic need. Enrollment criteria will be finalized at the time of protocol development to account for any updates to Kenyan national guidelines, but the central clinical criteria are as follows:

For all cisgender women

- Age  $\geq 18$  and  $\leq 30$  years old.
- Willing to undergo urine pregnancy tests.
- Has understood the information provided and has provided written informed consent before any study-related procedures are performed.
- HIV uninfected based on negative HIV rapid tests, according to Kenyan national algorithm.
- Normal renal function (estimated glomerular filtration rate  $>60$  mL/min).
- Hepatitis B surface antigen negative.
- No active, clinically significant medical or psychiatric conditions that, in the opinion of the investigators, would interfere with study participation .
- Lack of severe anemia (Hemoglobin  $>10$  g/dL).
- Willing to use DOT and come to clinic frequently for DOT PrEP for at least 10 weeks.
- Willing to have home visits for follow up.
- Has access to an active smartphone to allow off-site observation of dosing if unable to come to the clinic, or, as determined by the study staff, the participant resides in a close enough location to the clinic to permit a home visit if unable to come to the clinic. That is, potential participants without a smartphone may be enrolled in the study if investigator determines that the participant resides within reasonable distance from the clinic for a home visit in the case of a missed clinic visit.
- Intention to stay within the study site's catchment area for at least 10 weeks.
- Resides or works in catchment area with high speed internet coverage to permit video streaming.
- Not pregnant or breast feeding.
- Willing to use effective contraception during the study period.
- At low risk for HIV. *In Kenya, national guidelines define substantial risk for HIV and recommend PrEP be an option for individuals reporting: partner of HIV-infected person not on*

*ART or on ART for <6 months, >1 partner of unknown status, transactional sex, recent STI, recurrent PEP use, inconsistent condom use, or injection drug use. So, non-pregnant cisgender women reporting any of these factors will not be eligible for the study but will be linked for PrEP at clinic of choice including at Thika Site itself.*

- Willing to be randomized to non-daily PrEP and to come to the clinic frequently for DOT PrEP.
- Willingness and ability to be abstinent for at least 7 days after each vaginal biopsy visit.

### **3.2 Exclusion Criteria**

For all cisgender women

- Inability to give informed consent
- Positive screening HIV+ as determined by standard rapid serologic assays or suspected acute HIV infection in the opinion of the clinician. (Example signs and symptoms of acute HIV infection include combinations of fever, headache, fatigue, arthralgia, vomiting, myalgia, diarrhea, pharyngitis, rash, night sweats, and cervical or inguinal adenopathy.)
- Positive HBV surface antigen test at screening.
- Calculated creatinine clearance <60 ml/min.
- Any laboratory value or uncontrolled medical conditions that, in the opinion of the investigators, would interfere with the study conditions such as, heart disease and/or cancer.
- Prohibited concomitant medications are: investigational agents (within 30 days of enrollment), aminoglycosides, ganciclovir/valganciclovir, chronic high-dose acyclovir/valacyclovir (>800mg acyclovir or >500mg valacyclovir for >7 days), cyclosporine, amphotericin B, foscarnet, and cidofovir, and products with same or similar active ingredients as the study medications including TAF®, TRUVADA®, ATRIPLA®, COMPLERA®, EMTRIVA®, VIREAD®; or drugs containing lamivudine or adefovir, which are close analogs of FTC and tenofovir, respectively.
- Current or past use of PrEP (pre-exposure prophylaxis).
- Not willing to have home visits.
- Pregnant or plan to become pregnant in the next 6 months or unwillingness to use birth control.
- Currently breastfeeding.
- High risk of HIV infection (for example: sexually active with an HIV infected partner; engages in condomless intercourse with HIV-infected partners or partner of unknown status during the study; exchanges sex for money, shelter, or gifts; active injection drug use or during the last 12 months; newly diagnosed sexually transmitted infections in last 6 months).

### **3.3 Study Setting**

The proposed work will take place in Thika, Kenya. The site has extensive experience conducting large biomedical and PK studies and has a long-standing relationship with local public health authorities, HIV prevention advocates, and community leaders. Over the past decade, the Thika site has established a multi-disciplinary team focused on HIV prevention research (more than a dozen projects currently) and on provision of clinical care, including clinical studies involving follow up of pregnant cisgender women. The Thika site is a center of excellence for PrEP in Kenya and leads PrEP technical assistance to other clinics as part of Kenya national PrEP scale-up. As stated in the background section, the Thika site conducted the DOT PrEP PK study in breastfeeding cisgender women (see Figure 3), achieving 100% retention.

### 3.4 Recruitment and Prescreening Process

We will enroll a novel cohort of up to 54 evaluable non-pregnant, healthy, HIV-uninfected adult cisgender women volunteers. The experienced community outreach team at the study site in Thika employs community-based mobilization strategies, including working with the neighboring Thika District Hospital to identify pregnant cisgender women, engaging community health volunteers, gate keepers, peer to peer mobilization, youth peer providers and ambassador models, use of printed and electronica IEC materials, social media (WhatsApp and Facebook), radio talk shows in English and Kiswahili, active participation in local social events for information sharing, and partnering with learning institutions to give health talks and to provide study related information. The methods for recruitment proposed in this study are similar to those that were successfully used to conduct the pharmacokinetic study of PrEP in Breastfeeding cisgender women at the Thika site. From these strategies, we will identify those that are highest yielding and shift focus to primarily rely on them. The outreach team at PHRD is well-suited to develop innovative recruitment methods and collaborate with local partners to ensure that we achieve the accrual rate needed and enroll cisgender women who are highly dedicated to research procedures. The Thika team has >10 years of experience of conducting clinical trials, including in populations of cisgender women (Table 1). In many of the studies we have conducted, the Thika site has achieved the highest recruitment and data quality site compared to others in multisite/multinational studies – for example, in the Partners PrEP Study clinical trial of PrEP, and the MPYA Study. We will replicate and extend all of those previously proven recruitment strategies for this study.

**Table 1: Studies involving pregnant cisgender women at Thika**

Study and funding	Number of cisgender women enrolled
Partners PrEP (BMGF)	112
Partner Demo Project (R01MH0559907)	332
SCIP (R00HD076679)	74
MPYA (R01MH109309)	175
NuvaRing (R01HD077872)	122
GHS (CDC U48DP005013)	400

partnering with learning institutions to give health talks and to provide study related information. The methods for recruitment proposed in this study are similar to those that were successfully used to conduct the pharmacokinetic study of PrEP in Breastfeeding cisgender women at the Thika site. From these strategies, we will identify those that are highest yielding and shift focus to primarily rely on them. The outreach team at PHRD is well-suited to develop innovative recruitment methods and collaborate with local partners to ensure that we achieve the accrual rate needed and enroll cisgender women who are highly dedicated to research procedures. The Thika team has >10 years of experience of conducting clinical trials, including in populations of cisgender women (Table 1). In many of the studies we have conducted, the Thika site has achieved the highest recruitment and data quality site compared to others in multisite/multinational studies – for example, in the Partners PrEP Study clinical trial of PrEP, and the MPYA Study. We will replicate and extend all of those previously proven recruitment strategies for this study.

### 3.5 Co-Enrollment Guidelines

Participants in this study should not take part in any concurrent research studies that use drugs or medical devices while on follow up. Co-enrollment in observational or other studies may be allowable with approval of the site IoR or designee. Previous participation in the placebo arm of an HIV vaccine trial may be allowable with approval of Co-Chairs.

### 3.6 Retention of Study Participants

For this DOT pharmacokinetics study, high retention begins with the exclusion of participants who indicate a high likelihood of travel outside of the study area, who appear to lack dedication to the research process, or who may experience personal challenges with compliance with study visits. We will follow usual Kenyan clinical practices for notifying participants of their study follow-up visits, which include sending participants reminders via SMS messaging and telephone calls. In addition, an extensive tracing record at the time of study entry will be completed by a trained research staff member and will be used to trace participants who miss visits; the experienced community outreach team has established methods for successful participant tracing. As detailed in the Introduction Section, the Thika Site successfully recruited lactating cisgender women (and their infants, half <13 weeks of age) into a similar DOT PrEP PK study previously, achieving 100% retention for breastfeeding-month infant pairs and sample collection. The following approaches will be used to promote compliance and to achieve planned evaluable enrollment with pharmacokinetic sample collection.

**Medication calendar:** At study enrollment, subjects will be given a calendar for study visit appointments, dosing schedules, and to record unsolicited adverse events. For those interested and willing, visit schedule and reminders will be added to the calendar on their smartphones.

**Video streaming and phone reminders:** Flexible clinic scheduling will be available to promote high rates of follow-up and compliance and to minimize participant's burden. Video live streaming services via social media (e.g., WhatsApp, Skype, etc.) will be employed; only cisgender women with an active smart phone will be enrolled into the study to permit offsite observation of required DOT PrEP doses if needed. Use of live streaming will be supported with provision of weekly data/internet bundles consistent with the local IRB regulation. Remote DOT via video streaming is intended to increase compliance as well as minimize participant burden. Enrolled participants will receive a reminder message (sent via text message or phone call) the morning of every scheduled study visit. A one-month supply of back-up medication will be provided to participants at study enrollment to be used if the participant is unable to complete a visit at the clinic; all doses taken offsite will be directly observed by study staff via live video streaming on smart cell phone or computer via WhatsApp. For DOT doses taken via video streaming, participants will be asked to open their mouth afterwards to confirm swallowing.

**Home visits:** We will conduct home visits for patients unable to attend their scheduled clinic visits or procedures in order to promote compliance with study procedures. During home visits, study staff may conduct study procedures e.g., observing of dose taking or collection of study samples (blood, urine, hair) where applicable. Any offsite collection of study sample will follow the same safety standards followed at the clinic. **For this short-term intensive pharmacokinetics study where complete DOT compliance is pivotal for primary outcome measurement, only cisgender women who consent for home visits will be enrolled.**

### **3.7 Participant Withdrawal**

Regardless of the participant retention methods used, participants may voluntarily withdraw from the study for any reason at any time. The Site Investigator of Record or designee also may withdraw participants from the study to protect their safety and/or if they are unwilling or unable to comply with required study procedures. Participants also may be withdrawn if the study sponsor, government or regulatory authorities, or site IRBs/ECs terminates the study overall or at a specific site prior to 18 weeks.

Every reasonable effort will be made to complete final evaluations for participants who terminate from the study prior to the last study assessment or visit; study staff will record the reason(s) for all withdrawals from the study in participants' study records.

### **3.8 Replacement of Study Participants**

Data from participants who permanently discontinue study treatment will be used in analyses. Study participants who miss two consecutive scheduled doses, miss any pharmacokinetic samples, or permanently discontinue DOT PrEP will be replaced so that approximately 54 evaluable participants complete the study. No more than 20% of the target population (n=54) will be replaced. Data from subjects who discontinue prematurely will be used in analyses. Cisgender women who become pregnant will be replaced but will continue to be followed up to the end of their scheduled protocol study follow up. Seroconversions (unlikely, though possible) will not be replaced.

## **4 STUDY PRODUCT**

The study product is Descovy® formulated as tenofovir alafenamide (TAF) 25 mg/ emtricitabine 200 mg (FTC).

### **4.1 Study Product Formulation**

Each TAF-FTC tablet contains a co-formulation of TAF 25mg / FTC 200mg. An authorized study clinician will prescribe TAF-FTC as part of this study, with dosing instructions as described in this protocol.

#### **4.1.1 Study product storage**

Prior to dispensing, TAF-FTC tablets will be stored in the pharmacy in the original container. Each bottle contains a desiccant to protect the product from humidity. Study drug is to be stored at 68 °F to 77 °F (20 °C to 25 °C), with temperature excursions permitted between 15° to 30°C.

#### **4.2 Source of Study Product and Accountability**

Gilead Sciences will donate the study drug for this study. Study drug will be shipped to the investigational pharmacy and dispensed through the Thika Research Site pharmacy according to the research pharmacy policies and procedures of Kenya Pharmacy and poison board. The pharmacist of record will receive and inventory study medication, will dispense and track prescriptions, and will provide directions for returning unused medications for destruction according to local policy. The pharmacist of record will track the accountability of the study medications according to established procedures developed by the investigational pharmacy.

#### **4.2.1 Study product dispensation**

Two supplies of study drug will be dispensed for each participant. Both supplies will be dispensed in the original containers. Study personnel will be in possession of the main medication supply, which will be stored in a locked cabinet except during transportation to and from the directly observed dosing visits. This main supply will be enough for the entire 10-week DOT dosing period (enough medication to cover 10 weeks will be dispensed for the 70-84 day dosing window). Study personnel will record on the bottle the date that it is opened, and will ensure that opened bottles are used within 8 weeks. The locked cabinet will be in a temperature-controlled building, which is maintained at approximately 21°C. A second medication supply, a take-home supply, will be given to participants for non in-person dosing (video-streaming). Participants will be reminded to keep the medication in the original container with the desiccant, and to store it in a dry place with the cap tightly sealed. This take-home supply will be a maximum of one bottle of medication, with additional bottles given to participants when the current bottle is exhausted.

#### **4.2.2 Return and Destruction of Study Product**

Unused medications will be returned to the site study pharmacy at the end of the dosing periods or after a participant permanently discontinues study drug. The site pharmacy will account for and manage the returned medications in accordance with the local policies and procedures.

#### **4.3 Assessment of Participant Adherence with Study Product/Intervention**

Adherence will be assessed with directly observed dosing. All doses will be observed in person, when possible, at an agreed-upon private room at the research clinic or other predetermined location to maximize convenience for the participant. In circumstances where doses cannot be witnessed in person, doses will be witnessed by live audio-video communication or time-stamped videos . If video confirmation fails, this will be recorded as non-DOT dose.

#### **4.4 Concomitant Medications**

Concomitant medications will be evaluated on a case-by-case basis for interactions with the study medications. Certain medications are permitted, and other medications are prohibited as described in the sections that follow. Medications not listed in these sections will be evaluated for potential interactions with the study medications or procedures and a decision to enroll the subject will be made accordingly. Additionally, should a new concomitant medication be started during the study, the same evaluation will take place.

#### **4.5 Prohibited Medications**

Prohibited concomitant medications are: investigational agents, aminoglycosides, ganciclovir/valganciclovir, chronic high-dose acyclovir/valacyclovir, cyclosporine, amphotericin B, foscarnet, and cidofovir, and products with same or similar active ingredients as the study medications

including TRUVADA®, ATRIPLA®, COMPLERA®, EMTRIVA®, VIREAD®; or drugs containing lamivudine or adefovir, which are close analogs of FTC and tenofovir, respectively.

#### **4.6 Precautionary Medications**

Any medication or herbal supplement not listed under sections prohibited medication section will be evaluated on a case-by-case basis for interactions with the study medications. Should there be potential for serious interaction, based on the opinion of the investigators, the subject will not be invited to participate. Additionally, should a new concomitant medication be started during the study, the same evaluation will take place.

#### **4.7 Toxicity Management**

Safety related laboratory testing will be performed at study entry and at week 8 and or as indicated by clinician during follow up. If enrollment occurs more 30 days after screening, entry safety labs will be repeated. These include HIV rapid testing, complete blood count, HBV surface antigen, serum creatinine, and urine pregnancy test. Toxicity will be managed in consultation with a clinician on the protocol. The clinician may discontinue the study drug at any time if he/she feels that continued use would be harmful to the participant. The PSRT should be consulted when possible. The PSRT will be consulted when considering further holding or recommencing study medication.

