#### **4.8 HIV Seroconversion**

Frequent testing for HIV acquisition during the study period will allow prompt cessation of study drug in an HIV-infected participant, minimizing the risk that resistant virus will emerge. Therefore, HIV testing will be performed at all monthly study visits. HIV rapid testing and specimen collection will be completed prior to administration of study medication. Participants who have any reactive or positive HIV test result after initiating PrEP will be instructed to discontinue study drug immediately and will have further testing to clarify their HIV infection status, as described in Section 5.3. Any enrolled participant who is confirmed to have acquired HIV infection during the study will permanently discontinue study product and will be transitioned to a local HIV care clinic for appropriate follow-up and clinical management. Procedures for participants who acquire HIV infection are described in Section 5.3.

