**Clinic visit 10: Week 8 (Dose 56) visit:**

- HIV rapid test
- Urine pregnancy test (urine  $\beta$ HCG)
- Study bloodwork: WB, DBS, PBMC, plasma
- Finger stick for DBS
- Study urine
- Vaginal biopsy (all participants)
- Vaginal swab
- Hair collection
- Medical, sexual, contraception, antenatal and vaccine history review
- AE assessment
- Concomitant Medication Review
- DOT

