**Clinic visit 12: Week 10 Dose 70) visit:**

- HIV rapid test
- Study bloodwork: WB, DBS, PBMC, plasma
- Finger stick for DBS
- Study urine
- Safety Labs: Creatinine
- STI testing
- Medical, sexual, contraception, antenatal and vaccine history review
- AE assessment
- Concomitant Medication Review
- DOT

**Clinic visit 13: Post DOT PrEP visits (one week following dose cessation):** One visit at least 48 hours after the last DOT PrEP dose.

- Study bloodwork: WB, DBS, PBMC, plasma
- Study urine

**Clinic visit 14: Post DOT PrEP visits (Week 12-18):** One visit at least 14 days after visit above (i.e., the visit can occur any time between 2-8 weeks after the last DOT F/TAF PrEP which is between about week 12 and week 18 since enrollment)

- Study bloodwork: WB, DBS, PBMC, plasma
- Study urine
- Hair collection

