##### ***Blood***

A blood sample will be obtained at protocol specified visits to process plasma, whole blood, DBS, and PBMCs. On a given study day blood collection, up to 21mL of blood for study bloodwork will be drawn with no planned timing relationship with dosing. The blood will be collected from an arm vein by trained clinic staff according to study site policies and procedures.

The schedule of protocol visits and procedures are outlined in Table 2.

Table 2: Schedule of protocol visit schedule and procedures.

Timeline (weeks)	Screening	Entry	DOT PrEP Period (weeks)											Post DOT Period	
			W1		W2	W3	W4	W5	W6	W7	W8	W9	W10	W11	W12-18
			Day 4	Day 7											
Clinic Visits #		1	2	3	4	5	6	7	8	9	10	11	12	13	14
Procedure															
Informed consent	x														
Medical, sexual, contraception, antenatal history review, vaccine history	x	x	x	x	x	x	x	x	x	x	x	x	x		
Physical exam a	x														
Dispense back up PrEP medication e		x													
Issue medical calendar		x													
AE assessment		x	x	x	x	x	x	x	x	x	x	x	x		
Safety Labs a,c	x	[x]											x		
Urine βHCG a	x	[x]						x				x			
HBS Ag	x														
HIV-1 rapid test a	x	[x]						x			x				
Hair collection							x			x		x			x
hDNA	x		x												
Study Bloodwork d (WB, plasma, DBS, PBMC)*PBMC is collected bi-weekly		x	x	x	x	x	x	x	x	x	x	x	x	x	x
Vaginal tissue f			x	x			x					x			
Vaginal swab		x	x	x			x				x		x		
DBS by fingerstick			x	x			x				x		x		
Study Urine d		x	x	x	x	x	x	x	x	x	x	x	x	x	x
Concomitant Medication Review	x	x	x	x	x	x	x	x	x	x	x	x	x		
STI testing (CT,GC, syphilis, HSV-2)		x											x		
DOT b		x	x	x	x	x	x	x	x	x	x	x	x		

[x] Indicated if screening occurred more 30 days before planned enrollment. The screen and entry visits must be ≤ 30 days apart.

a. Safety labs or vitals can be performed as needed at any time

b. DOT performed if applicable per randomization schedule

c. Protocol-specified safety labs include: CBC, HbAg, Creatinine clearance, in addition to monthly HIV testing and urine pregnancy tests.

d. Study Bloodwork: WB, DBS, PBMC, plasma and all available blood cell types; Study Urine: endogenous molecules such as nucleosides.

\*PBMC is collected bi-weekly (baseline, week 2, 4, 6, 8, 10)

e. Study medications will be dispensed as described

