### **6.8.4 Creatinine Clearance**

Participants who enroll with a Grade 2 CrCl will discontinue study drug only if there is an increase in severity (to Grade 3 or 4). If the calculated creatinine clearance is  $<60\text{mL/min}$ , it should be confirmed ideally within approximately one week of the receipt of the results. Study drug should be halted temporarily awaiting confirmatory testing. The PSRT should be consulted for further guidance about restarting study drug for participants who fail to have a confirmed test within two weeks of receiving the initial result. If the calculated creatinine clearance is confirmed to be  $<60\text{ mL/min}$ , the study drug must be temporarily discontinued. The participant will be monitored as deemed clinically necessary in consultation with the PSRT until level returns to baseline (screening value) or stabilizes.

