### **Protection against risks related to TAF-FTC PrEP**

All participants will have HIV testing, creatinine testing, hepatitis B, and urine pregnancy testing at baseline. Only cisgender women with creatinine clearance >60 mL/min and uninfected with hepatitis B will be enrolled. Testing of volunteers for HBV-infection is conducted to protect subjects from HBV-associated hepatitis flares when study drugs are withdrawn. Breastfeeding will not be allowed to prevent risks to nursing infants. We will exclude subjects who have serious underlying illnesses such as cancer and heart disease. All participants will be counseled about potential side effects at enrollment and at each follow up visit, and they will be reminded that the side effects are self-limiting within 1-2 weeks. Subjects will be followed with clinical laboratories at entry and 10 weeks (serum creatinine, complete hematology, monthly pregnancy urine test) and more frequently with interviews to assess tolerability and safety over the course of the study, including during directly observed dosing. Participants will be tested for HIV infection at any point during the study as needed, and prior to and at the final visits of the dosing periods.

The most likely risks associated with TAF-FTC in HIV-negative persons appear to be reversible gastrointestinal complaints, headache, and/or weight decrease. These side effects are most likely mild and reversible. There is a remote risk of serious side effects including renal injury, lactic acidosis with hepatomegaly and steatosis, bone pathology, hypophosphatemia, hepatitis, pancreatitis, and there are possible side effects not listed here, or possible unforeseen long-term complications. We believe the risk of these serious side effects is remote given the rarity of the events during long-term treatment and PrEP in previous studies. We have designed the inclusion and exclusion criteria to exclude subjects who might be at higher risk of these toxicities. We have also designed a monitoring strategy for early detection of side effects and for quick study drug discontinuation, if needed, to protect subjects.

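### Section 4.7 sets on-treatment safety labs at week 8, but the visit lists and Section 8.5 set them at week 10, when almost no nominal doses remain for the Section 6.8.4 creatinine hold to stop

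*Combined protocol and SAP*

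**What the plan says.** Four places in the protocol set the time of safety laboratory testing after dosing starts.

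- **Section 4.7:** "Safety related laboratory testing will be performed at study entry and at week 8 and or as indicated by clinician during follow up". The tests it then lists include CBC, HBsAg and serum creatinine, but that list may refer only to the entry labs mentioned just before it.
- **Section 5.2.2:** The list under "Clinic visit 10: Week 8 (Dose 56) visit" has an HIV test, a urine pregnancy test, study blood and a biopsy, but no creatinine or CBC. The list under "Clinic visit 12: Week 10 Dose 70) visit" has "Safety Labs: Creatinine" and no CBC.
- **Table 2:** The Safety Labs row is marked at screening, conditionally at entry, and at week 10. Footnote c gives the panel: "Protocol-specified safety labs include: CBC, HbAg, Creatinine clearance, in addition to monthly HIV testing and urine pregnancy tests".
- **Section 8.5:** "Subjects will be followed with clinical laboratories at entry and 10 weeks (serum creatinine, complete hematology, monthly pregnancy urine test", with the closing bracket following.

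The result of the test drives a stopping rule. When a calculated creatinine clearance falls below 60 mL/min, Section 6.8.4 says: "Study drug should be halted temporarily awaiting confirmatory testing". Confirmation is ideally within about a week, and restarting is discussed with the PSRT if no confirmed test arrives within two weeks.

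**The concern.** No reading makes all four places agree on time, and they also differ on the panel. Staff at Thika cannot tell from the protocol whether the scheduled on-treatment creatinine belongs at week 8, at week 10 or at both, or whether a CBC goes with it.

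The choice of week matters because a temporary halt and a restart presuppose doses still to come. Dosing lasts 10 weeks. If week 10 governs, the only scheduled creatinine after the first dose is taken as dosing ends. Section 8.5 describes the monitoring as meant to catch side effects early and stop drug promptly; a single scheduled test at the end of dosing does little for that. Safety is also the first primary objective, and Section 6.3 captures laboratory events of Grade 2 and above, so the timing and panel determine which laboratory events can be seen.

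**Working it through.** The plan gives no figure of its own here. The check compares the texts and then counts the doses left after each candidate draw.

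**Which week do the texts support?** Section 4.7 says week 8. The visit-12 list and Section 8.5 say week 10, independently of each other. The Table 2 mark also falls under week 10, but column alignment in the text I read is imperfect: the last vaginal-tissue mark falls under week 9, although footnote f says week 8. I treat Table 2 as supporting evidence only.

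**Inputs.** Dosing runs for days 1 to 70 (10 weeks, Section 5.2). Dosing days are daily; Monday, Tuesday, Thursday and Friday; or Monday and Tuesday (Section 2.5). Planned totals are 10 × 7 = 70, 10 × 4 = 40 and 10 × 2 = 20. Assumption: day 1 is a Monday, so days 56 and 70 are Sundays.

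**Formula.** Doses left after a draw on day t = number of scheduled dosing days d with t < d ≤ end day. If the draw is pre-dose and the result comes the same day, day t itself also counts.

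| Draw and end of dosing | 7/week | 4/week | 2/week |
|---|---|---|---|
| Day 70, end day 70, post-dose | 0 | 0 | 0 |
| Day 70, end day 70, pre-dose with same-day result | 1 | 0 | 0 |
| Day 56, end day 70, post-dose | 14 | 8 | 4 |
| Day 56, end day 70, pre-dose with same-day result | 15 | 8 | 4 |
| Week-10 visit 10 days early (day 60), end day 70 | 10 | 5 | 2 |
| Week-8 visit 10 days late (day 66), end day 70 | 4 | 2 | 0 |
| Day 70, end day 84 | 14 | 8 | 4 |
| Day 56, end day 84 | 28 | 16 | 8 |

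The post-dose week-8 figures are 14/70 = 8/40 = 4/20 = 20% of each arm's planned doses.

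**Pre-dose or post-dose?** Section 4.8 says "HIV rapid testing and specimen collection will be completed prior to administration of study medication". If that covers the visit-12 draw, the pre-dose row applies. Section 9.1 leaves PK sampling untied to dosing time, so the post-dose row is also possible.

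**Sensitivity.**
- The 10-day visit window (Section 5.2.2) has no stated direction, so the table shows both extremes.
- The day-84 rows are upper bounds from the 70-84 day window in Section 4.2.1. They assume dosing continues at full frequency, although the dispensed supply covers 10 weeks.
- With both visits on their nominal day, week 8 leaves 14, 8 and 4 more doses than week 10 in every case: 14 − 0, 15 − 1 and 28 − 14 in the daily arm; 8 − 0 and 16 − 8; 4 − 0 and 8 − 4.
- The start weekday hardly matters. Any 14 consecutive days hold 14, 8 and 4 doses. A different start could at most make day 70 a dosing day in the other arms, giving one dose there if drawn pre-dose.

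**The case against.** The strongest reply is that the conflict is one stale word. Sections 7.4 and 9.1 also carry eight-week wording although dosing lasts ten weeks, so week 8 in Section 4.7 may be a leftover end-of-dosing time point. Changing it to week 10 would reconcile the timing, and no section schedules creatinine at both weeks. This is plausible and cannot be excluded. It would repair the text, but the hold would still have almost nothing to act on from a scheduled test.

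A reader might also infer that the hold cannot work at all. The documents do not support that. Sections 4.7 and 5.2 and Table 2 footnote a allow labs as needed, the clinician may stop drug at any time, adverse events are assessed at every dosing-period visit, and the windows can leave doses after a week-10 draw. Confirmation and follow-up under Section 6.8.4 also still work after week 10. The limitation concerns scheduled testing on the nominal calendar. As-needed testing normally requires a prompt, and an asymptomatic creatinine change may give none.

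Nor does the visit-12 list prove that no CBC would be drawn at week 10; it disagrees with two other places that include one. Divergence between sites is not an issue, because there is only one site.

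Finally, the women are aged 18-30, healthy, and enter with clearance above 60 mL/min, and the protocol regards serious toxicity as remote. That stands: doses remaining measure the opportunity to act, not harm.

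**Conclusion.** The inconsistency is real and should be corrected. Timing conflicts between Section 4.7 and the visit-12 list, Section 8.5 and Table 2; the panel conflicts between the visit-12 list and Section 8.5 with Table 2 footnote c. On the week-10 schedule, the scheduled creatinine gives the Section 6.8.4 hold no nominal doses to stop, or one in the daily arm at best. On the week-8 schedule it gives 14, 8 and 4.

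These counts rest on a Monday start, visits on their nominal day and dosing ending on day 70. The documents give no expected rate of clearance below 60 mL/min, so the number of women affected cannot be estimated. A conclusion that participants would be harmed, or that the descriptive safety objective fails, is not supported: a week-10 value still contributes to that objective.

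**What to change.** 1. Add serum creatinine and CBC to visit 10 (week 8), as the timing in Section 4.7 implies. Study blood is already drawn at that visit, and Section 5.2.2 already uses the venous sample for safety laboratories.
2. Keep week 10 as the end-of-dosing check and add CBC to the visit-12 list.
3. Make Sections 4.7, 5.2.2 and 8.5 and Table 2 state the same weeks and the same panel.
4. State that HBsAg is tested at screening (repeated at entry if needed) and is not part of the on-treatment panel. Footnote c now includes it and Section 8.5 does not.

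**Cost.** Amendment wording plus 54 extra creatinine and 54 extra CBC assays. Section 3.8 caps replacement at 20% of 54 = 10.8, so at most 10 women, giving at most 64 of each if all reach week 8. No extra visit or venepuncture is needed.

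**Downside.** A week-8 value below 60 mL/min halts drug pending confirmation. A hold lasting the full week would skip 7, 4 or 2 scheduled doses, and two consecutive missed doses trigger replacement under Section 3.8. The entry criteria suggest this would be uncommon, but the amendment should say how such a woman is handled.
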